12.5.2 Missing with respect to the primary endpoint

A subject in the ITT population will be defined as missing with respect to the primary endpoint (lost to follow up for the purposes of analysis of the primary endpoint) if the subject withdrew, discontinued consent or was lost to follow up prior to 3 month window for CMV disease without having reached the primary endpoint.

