Study Design: This is a prospective, randomized, multicenter trial of preemptive therapy vs. prophylaxis for prevention of CMV disease in R-D+ liver transplant patients. Patients meeting study criteria and who have provided informed consent will be randomized within 10 days of transplant to receive in an open label design, either antiviral prophylaxis with valganciclovir 900 mg orally once daily or preemptive therapy (weekly monitoring for CMV viremia by plasma PCR) for 100 days post- randomization with initiation of oral valganciclovir 900mg orally twice daily at onset of CMV viremia and continued until plasma PCR is negative on two consecutive weekly PCR tests). Valganciclovir dosages will be adjusted for renal dysfunction. Study participants will be followed during the intervention period (100 days post randomization) and until 12 months post-transplant for CMV disease, toxicity, and clinical outcomes (opportunistic infections, rejection, graft loss and mortality). All-cause mortality, rejection episodes, graft loss and retransplantation, opportunistic infections , need for dialysis, and post-transplant malignancies will be assessed at one year and until study closure (no longer than 7 years from enrollment

maximum). Additionally, the impact of the two CMV prevention strategies on CMV-specific cellular and humoral immune responses will be evaluated at 100 days after randomization, and 6 and 12 months post-transplant. A minimum of 176 subjects will be enrolled in the study. Allowing for over-enrollment for dropouts, withdrawals and deaths prior to 6 months, up to 205 subjects may be enrolled to achieve the target enrollment with one year follow up.

Estimated Time to Complete Enrollment: Approximately 3.5 years

Schematic of Study Design:

Pre or post liver transplant patient with CMV negative serology

Day of enrollment

- Medical record screening for inclusion/exclusion criteria
- Informed consent
- Study specific screening procedures:
- Safety labs (must be within 48 hours of randomization)
- Verification of inclusion/exclusion criteria

Randomization (study day 1) must be within 10 days of transplant

Preemptive therapy

- CMV monitoring (weekly)
- VGCV upon positive PCR
 - AE/SAE monitoring
 - Clinical evaluations
 - Safety Labs
 - Immune assay (day 100)

Prophylaxis

VGCV

Discontinuation of antiviral

Prevention strategy

Clinical evaluations
Immune assay (6 month and 12 month)

100 days

Final Visit (12 months post-enrollment)

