2.2 Rationale

There are two major strategies for CMV prevention in clinical setting; prophylaxis and preemptive therapy(6). With the strategy of prophylaxis, antiviral drug is administered to all patients at any risk for CMV disease, usually for 100 days post-transplant. In preemptive therapy, antiviral drug is specifically targeted to patients deemed to be at highest risk for CMV disease, as determined by the detection of early viremia. Prompt initiation of antiviral therapy at the first detection of early viremia prevents progression to CMV disease (7-9). Each of the strategies has been studied individually and been shown to be effective for the prevention of CMV disease (compared to either placebo or no prevention strategy), but there is a striking paucity of direct comparative studies. The relative benefit of one strategy versus another has long been debated and there is strong support within the transplant community for a well-designed direct comparison of the two strategies for prevention of CMV disease in high-risk R-/D+ patients. This study will test the null hypothesis that the incidence of CMV disease in the prophylaxis intervention group is equal to the incidence in the preemptive therapy group. Defining the optimal strategy for the prevention of CMV is expected to have significant clinical benefit in the management of transplant recipients and to provide important insight into the immunologic mechanisms that are responsible for control of CMV in this setting.

Although the approach of preemptive therapy has been shown to be useful for prevention of CMV in transplant patients in previous studies, the totality of evidence supporting its use is more limited than for prophylaxis. As a result, prophylaxis with valganciclovir (given its high oral bioavailability and convenient once daily dosing) has emerged as the dominant strategy for the prevention of CMV in R-/D+ transplant patients (10, 11). However, late-onset CMV disease, defined as CMV disease occurring after 3 months post-transplant is now

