recognized as a significant complication with the use of prophylaxis, particularly in R-/D+ patients (12-15). An evidence-based review showed that the incidence of CMV disease and specifically that of late-onset CMV disease in the valganciclovir era in these patients is substantially higher with prophylaxis than preemptive therapy (16). Overall, CMV disease has been documented in 2.6% of patients receiving preemptive therapy in the current era and in contrast to prophylaxis, it occurs largely within 100 days of transplantation (16). The frequency of CMV disease with prophylaxis and preemptive therapy based on studies in recent literature is summarized below. While, there are significant limitations of these data, including the fact that these are non-comparative studies and include heterogeneous transplant populations, there is a clear trend towards higher rates of CMV disease in patients who received prophylaxis compared to preemptive therapy.

CMV disease rates with antiviral prophylaxis for 3months						
Study	Sample size	Type of transplant	Drug	R/D status	Follow up	CMV disease (%)
(9)	177	Liver	VGCV	R-/D+	12 mo.	19
(17)	29	Liver	VGCV	R-/D+	12 mo.	30
(12)	38	Liver	OGCV	R-/D+	12 mo.	26
(2)	163	Kidney	VGCV	R-/D+	12 mo.	36.8
(18)	158	Kidney-panc	VGCV	R-/D+	12 mo.	39
(19)	25	Kidney	VGCV	R-/D+	12 mo.	40
(13)	67	Liver	OGCV/VGCV	R-/D+	12 mo.	28
(14)	54	Liver	VGCV	R-/D+	19mo.	26
(15)	39	Kidney	OGCV	R-/D+	12 mo.	31

CMV disease rates with preemptive therapy						
Study	Sample size	Type of transplant	Drug	R/D status	Follow up	CMV disease (%)
(20)	41	Liver	OGCV	R-/D+	4 mo.	0
(21)	22	Liver, Kidney	VGCV	R-/D+, R+	12 mo.	0
(22)	36	Liver	OGCV/ VGCV	R-/D+	20.4 pt/yr	0
(23)	42	Kidney, KP	VGCV	R-/D+	12 mo.	0
(24)	36	Liver	VGCV	R-/D+	62.8 pt/yr	0
(25)	11	Liver	VGCV	R-/D+	18 mo.	0
(26)	30	Liver	VGCV	All	12 mo.	0
(27)	36	Kidney	VGCV	R-/D+,R+	12mo.	5.5

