12.4.2 Missing data

Sensitivity analysis employing imputation of missing values will be carried out for efficacy and safety endpoints as appropriate. The type of imputation is specified under the analysis section for each end point where imputation is employed. In addition, imputation will be employed for missing or incomplete dates for the onset of adverse events. For selected analyses, a complete date is necessary to determine whether or not an adverse event began after study treatment. In cases where an incomplete onset date is provided in the case report form (CRF), the missing components will be defined as follows:

- Missing day, month and year present: If month and year are the same as the first treatment dose month and year, the day will be assumed to be the same as the first dose day. Otherwise, the day will be assumed to be the 15th.
- Missing day, month and year: The date will be assumed to be the same as the first treatment dose date. If the imputed date is after the resolution date, the imputed onset date will be assumed to be the same as the resolution date.
- Severity and causality of adverse events occurring on or after the start of study drug are imputed when missing events for which causality was unknown or not recorded will be included in the summary of study drug related events.

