12.5 Primary outcome measures

12.5.1 Definition

The primary endpoint is the incidence of CMV disease within 12 months post-transplant. This endpoint will include all reported occurrences of CMV disease as adjudicated by the endpoint committee and/or investigator-determined CMV disease. The latter endpoint will include all reported occurrences if CMV disease by the investigator, regardless of whether they met the protocol definition of CMV disease.

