12.5.3 Primary outcome analysis

12.5.4 Primary end point-CMV disease [ITT group] includes all randomized subjects]

The primary endpoint is CMV disease. The primary analysis is the Cochran-Mantel-Haenszel [CMH]. Incidence rates will be compared and point estimates and confidence intervals for the incidence-rate ratio and difference, along with attributable or prevented fractions will be calculated for the two regimens. The analysis will be repeated, controlling for induction antilymphocyte therapy. Within-stratum statistics will be shown as well as the combined with Mantel-Haenszel estimate. Subjects that die or are lost to follow up without evidence of CMV disease will be considered as 'no disease' for this analysis. All randomized subjects will be

included in the denominator. An additional analysis will be performed in which all lost to follow up subjects will be considered as 'CMV disease'.

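### Section 12.5.2 stops the definition of loss to follow-up at 3 months although the primary endpoint runs to 12 months, so it conflicts with the 'lost = CMV disease' analysis in 12.5.4

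*Combined protocol and SAP*

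**What the plan says.** - **Endpoint (12.5.1):** "The primary endpoint is the incidence of CMV disease within 12 months post-transplant". Section 7.10 puts the exit visit at 12 months, with two weeks either side.
- **Missing (12.5.2):** a subject in the ITT population is missing "if the subject withdrew, discontinued consent or was lost to follow up prior to 3 month window for CMV disease", provided the endpoint has not been reached. A parenthesis in the same sentence says this is what lost to follow-up means in the primary endpoint analysis.
- **Main coding (12.5.4):** "Subjects that die or are lost to follow up without evidence of CMV disease will be considered as" no disease, and every randomized subject stays in the denominator.
- **Worst-case check (12.5.4):** "An additional analysis will be performed in which all lost to follow up subjects will be considered as" CMV disease. No cut-off is given and 12.5.2 is not cited.
- **Imputation in general (12.4.2):** "The type of imputation is specified under the analysis section for each end point where imputation is employed". For the primary endpoint, 'lost = CMV disease' is the only alternative to the main coding that the plan gives.

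**The concern.** The period that 12.5.2 leaves out is the one the trial was designed around. Section 2.2 dates late-onset disease from 3 months after transplant and describes it as "recognized as a significant complication with the use of prophylaxis, particularly in R-/D+ patients"; it is also a secondary endpoint (3.2.2).

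A worst-case recoding asks whether the result depends on treating unseen outcomes as disease-free. If it covers only losses before month 3, it cannot answer that for the other 9 of the 12 months. The trial is open label, so loss after month 3 need not be balanced between arms. Two analysts could also build different tables from 12.5.2 and 12.5.4, and the choice would be made after the data are seen.

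**Working it through.** **Reading the sections together.** Take a subject who leaves at month 5 without CMV disease.

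| Rule | Treatment of this subject |
|---|---|
| 12.5.4, main analysis | No disease, in the denominator |
| 12.5.4, 'lost = CMV disease', read alone | Recoded as CMV disease |
| 12.5.4, 'lost = CMV disease', with the 12.5.2 definition | Not lost, so not recoded |

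The last two rows conflict, and no other section decides between them. Section 12.6.1.1 uses 3 and 12 months as separate time points, so the 3-month cut-off cannot be read as another name for the 12-month visit. The main analysis gives the same answer on either reading, because a subject without recorded disease counts as no disease whatever the date of loss.

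**The plan's own figure.** Section 12.1 states 80 per group, 20% vs 5%, two-sided Fisher test at 0.05, power 80%. Exact enumeration gives 79.3%, so the figure reproduces. It is context only and is not disputed.

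**Illustration.** The documents give no rate, timing or split by arm for late loss, so the losses below are assumptions.

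- Enrolled: 176/2 = 88 per arm (minimum), or 205/2, about 102 per arm (maximum).
- Events at 88 per arm: 0.20 × 88 = 17.6, taken as 17 or 18; 0.05 × 88 = 4.4, taken as 4.
- Events at 102 per arm: 0.20 × 102 = 20.4, taken as 20; 0.05 × 102 = 5.1, taken as 5.
- Test: unstratified CMH without continuity correction. With n per arm, m total events and a events under prophylaxis, chi-square = (a − m/2)² / V, where V = m(2n − m) / [4(2n − 1)].

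Worked case, 17 vs 4 at n = 88: m = 21, V = 21 × 155 / (4 × 175) = 4.65, chi-square = 6.5² / 4.65 = 9.09, p = 0.0026.

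If late losses are recoded as disease (prophylaxis/preemptive), the CMH p-values, with Fisher in brackets, are:

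| Late losses recoded | 88 per arm, 17 vs 4 | 88 per arm, 18 vs 4 | 102 per arm, 20 vs 5 |
|---|---|---|---|
| None (3-month definition) | 0.003 (0.004) | 0.002 (0.002) | 0.001 (0.002) |
| 12/12 | 0.025 (0.037) | 0.017 (0.025) | 0.014 (0.021) |
| 0/4 | 0.053 (0.083) | 0.034 (0.054) | 0.028 (0.044) |
| 2/6 | 0.068 (0.103) | 0.046 (0.070) | 0.037 (0.056) |
| 4/8 | 0.083 (0.122) | 0.057 (0.085) | 0.046 (0.068) |
| 0/5 | 0.090 (0.136) | 0.061 (0.093) | 0.049 (0.074) |

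Equal loss leaves the result standing. An excess of 4 to 5 in the preemptive arm brings p to around 0.05; the side on which it falls depends on rounding, the test and total enrollment. If loss were equally likely in both arms, all four of four losses would fall in the preemptive arm with probability 0.5⁴ = 0.06. Under the 3-month definition the first row is reported in every one of these cases.

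**The case against.** The strongest reply is that 12.5.4 speaks of all lost subjects, does not cite 12.5.2, and uses the same term just before for the main rule, where it plainly covers any loss. Read by itself it already does the right thing. That stands as a fair reading of 12.5.4, and it is why the fault is a conflict between two sections and not a settled omission. It does not remove the fault, because 12.5.2 defines the term expressly for this analysis.

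A second reply is that late loss is partly dealt with elsewhere. Records are reviewed and subjects or outside physicians may be contacted (7.7.3), which should keep true loss low. Length of CMV evaluation is summarised (12.4.5), and time-to-event analyses are planned (12.5.5, 12.6.1.1, 12.7.1.1). This limits the likely size. But 12.7.1.1 censors losses, and none of these analyses is planned as a worst-case check.

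Two stronger readings are tempting and should not be drawn:

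- **That the plan itself expects loss after month 3.** The Protocol Summary says "Allowing for over-enrollment for dropouts, withdrawals and deaths prior to 6 months, up to 205 subjects may be enrolled". That wording places no loss after month 3, mixes in deaths, and the time limit may attach to deaths alone. The allowance, (205 − 176)/205 = 14%, is not a late-loss rate.
- **That an excess of four late losses is a fixed tipping point.** It crosses 0.05 on CMH from 17 vs 4, but at 0/4 and 2/6 it does not from 18 vs 4. At 102 per arm, none of the excess-of-4 splits shown crosses on CMH.

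**Conclusion.** The point holds as a conflict in the text. A 3-month definition of loss sits under a 12-month endpoint and, applied as written, removes months 3 to 12 from the only worst-case check on the primary endpoint. A reader might infer that the primary result or its power is compromised. The documents do not support that: the main CMH coding and the sample size do not depend on 12.5.2.

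The size is modest and conditional. With the assumed 20% and 5% event rates, balanced late loss changes no conclusion, and only an excess of about 4 to 5 late losses in the preemptive arm would bring p to around 0.05. These figures rest on assumed losses and on an unstratified test. The change should be made because the rule is wrong as stated and the correction is very cheap, not because a reversal is likely.

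**What to change.** 1. In 12.5.2, define missing as withdrawal, discontinued consent or loss before the 12-month visit window (two weeks either side) with no prior CMV disease event.
2. In 12.5.4, state that the 'lost = CMV disease' analysis uses exactly that set, in both arms.
3. State in advance whether subjects withdrawn for retransplantation after day 30 belong to the set. Section 7.8.2 stops CMV endpoint collection for them, so their status is unknown, and the model that censors them (12.5.5) sits under the modified ITT heading. If they are left out, also show the result with them included. Section 6.2.5 expects fewer than 2% of such cases, that is fewer than 0.02 × 176 = 3.5 subjects.

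Optional: say in 12.6.1.1 which missing-data definition applies to late-onset disease, and split the disposition table in 12.4.3 into loss before and after month 3.

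Cost: a sentence or clause in each place. No new data or model is needed, since the date of last contact is already used in 12.4.5 and recorded for withdrawals (5.4.3.2). The downside is a possibly less favourable worst-case result.

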12.5.3 Primary outcome analysis

12.5.4 Primary end point-CMV disease [ITT group] includes all randomized subjects]

The primary endpoint is CMV disease. The primary analysis is the Cochran-Mantel-Haenszel [CMH]. Incidence rates will be compared and point estimates and confidence intervals for the incidence-rate ratio and difference, along with attributable or prevented fractions will be calculated for the two regimens. The analysis will be repeated, controlling for induction antilymphocyte therapy. Within-stratum statistics will be shown as well as the combined with Mantel-Haenszel estimate. Subjects that die or are lost to follow up without evidence of CMV disease will be considered as 'no disease' for this analysis. All randomized subjects will be

included in the denominator. An additional analysis will be performed in which all lost to follow up subjects will be considered as 'CMV disease'.

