The participating sites are currently using valganciclovir prophylaxis for 100 days after liver transplantation for CMV prevention as standard of care with drug costs charged to the patient or third-party payers as part of routine clinical care. In this study, one group of subjects will continue to receive standard of care (valganciclovir prophylaxis) and the other group will receive preemptive therapy with valganciclovir only upon evidence of CMV infection. For the group randomized to preemptive therapy, the drug use is estimated to be 43% less. No additional costs for valganciclovir use for study purposes will be incurred by the participating institution, subject or another party for participants randomized to either preemptive therapy or to prophylaxis.

Use of model for end-stage liver disease (MELD) scoring system as the basis for prioritizing organ allocation by the United Network for Organ Sharing in the current era has led to a substantially higher number of patients undergoing transplantation who have renal dysfunction or are requiring dialysis than time in the previous years (53,54). In order that our study is considered representative of liver transplantation practices at present and in order for our findings to be generalized to the transplant population undergoing in current clinical settings, it is important to include liver transplant subjects that require dialysis. Data in patients on dialysis have documented no pertinent issues that could influence the pharmacokinetics and bioavailability of valganciclovir in the study subjects (55). Furthermore, all study sites are currently using valganciclovir in dialyzed patients as standard of care. Receipt of dialysis has no effect on CMV disease rate in transplant recipients. However, given higher post-transplant mortality in patients receiving dialysis (56), subjects will be stratified by receipt of dialysis and sample size calculations will take into consideration the mortality within the first year.

We propose to conduct a randomized trial comparing prophylaxis versus preemptive therapy for the prevention of CMV disease in R-/D+ liver transplant recipients. The key goals of the study are to assess the efficacy of the 2 clinically used approaches for CMV prevention and not the efficacy of the drug per se. In this regard, this is a strategy trial based on the clinical practice of medicine using a drug that is currently the standard of care in these patients.

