5.4.2 Randomization

Subjects will be randomized in 1:1 allocation to one of 2 study groups. All subjects that have met all criteria for study enrollment and have given written informed consent will be randomized via a web-based randomization system at the study web-portal.

The study team member randomizing the subject will get an immediate message providing group assignment. Randomization at each site will be stratified by: 1) the receipt of lymphocyte depleting induction and 2) dialysis at time of randomization. Randomization will occur as soon as it is feasible, but no later than 10 days after transplantation. Inadvertently randomized

subjects who do not meet the inclusion/exclusion criteria or those who are withdrawn prior to receiving the study drug will be replaced.

Subjects receiving lymphocyte depleting induction at the time of transplantation (even for those randomized to the preemptive therapy group) may receive up to 10 days of antiviral therapy with valganciclovir or IV ganciclovir after transplantation. Additionally, if the treating physician prescribes valganciclovir or IV ganciclovir for any length of time prior to randomization, it will not preclude subject enrollment. For subjects assigned to the prophylaxis group, the first dose of study drug should be given on the day of randomization regardless of lymphocyte induction. For subjects in the preemptive group that have received lymphocyte depleting induction, antiviral therapy with valganciclovir or IV ganciclovir will be given for ten days then stopped. Subjects that have not received lymphocyte depleting induction, but have received doses of valganciclovir or IV ganciclovir after transplantation prior to randomization, will have the pre-randomization treatment stopped and begin study treatment on randomization day based on their assigned group.

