12.2 Treatment groups

Subjects will be randomized into one of the two groups in 1:1 ratio. Prophylaxis group will receive VGCV for 100 days and preemptive therapy group will undergo weekly CMV PCR screenings and receipt of VGCV following a positive CMV PCR test. A stratified, blocked randomization scheme will be utilized in order to keep the sample sizes similar in both groups.

Subjects at each site will be stratified by receipt of anti-lymphocyte induction therapy and renal dialysis at the time of randomization. Subjects will be consecutively entered.

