12.6 Secondary outcome measures

12.6.1 Clinical outcomes

12.6.1.1 Incidence of late onset CMV disease [adjudicated]

The incidence of adjudicated CMV disease will be determined at the 3 and 12-month time points (late-onset CMV disease) using an analysis similar to that specified for the primary analysis of the primary endpoint and, in addition, will include separate subset analyses for CMV syndrome and CMV tissue invasive disease. The analysis will be a Cochran-Mantel-Haenszel test of the significance of the odds ratio, while controlling for the use of induction antibody therapy and renal dialysis. In addition potential prognostic factors, such as allograft rejection will be examined with a Cox proportional hazards model applied to the ITT and modified ITT populations. This analysis will be used to test the presence of a treatment effect while controlling for the various prognostic factors entered into the model. Results will be reported as the hazard ratio comparing two groups.

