12.6.1.3 Bacterial, fungal and non-CMV viral infections

Invasive fungal infections, major bacterial infections and non-CMV viral infections will be analyzed. These infections are outlined in the manual of operations. The analysis of incidence of an opportunistic infection will be performed using a Chi Square test or Fisher Exact in the modified ITT population. Results will be reported as the p -value and the 95% confidence interval for the difference in the rates of invasive fungal, major bacterial or viral infections; the analysis will be repeated using a CMH test stratified by receipt of induction therapy. The analysis will include an assessment of baseline comparability of the comparison groups and will incorporate variables not adequately controlled by randomization. The initial episode of major infection will be evaluated in a time dependent Cox model with the end point being the date of first major infection. The starting point will be date of transplantation and the infection free survival functions will be compared between the two regimens adjusted for cluster [site]. Subjects will be censored at death and study termination/withdrawal. Multiple infection episodes will be evaluated by comparing the total 1 year episodes per person day of follow up between the two regimens. The analysis will be repeated controlling for receipt of anti-lymphocyte induction and renal dialysis. The type of infection (major bacterial, fungal, non- CMV viral) will be compared between the two regimens using a CMH test, non-stratified and controlled for induction antilymphocyte therapy and renal dialysis. Summary tables listing the type of opportunistic infections for each regimen will be presented.

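### The primary CMH test in 12.5.4 names no strata and is repeated for induction only, although randomization is stratified by induction and dialysis; the effect is small and conservative, but the strata should be stated

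*Combined protocol and SAP*

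**What the plan says.** Section 5.4.2: "Randomization at each site will be stratified by: 1) the receipt of lymphocyte depleting induction and 2) dialysis at time of randomization". Section 12.2 repeats this: "Subjects at each site will be stratified by receipt of anti-lymphocyte induction therapy and renal dialysis at the time of randomization". The background (2.2.2) gives the reason for the dialysis factor: "given higher post-transplant mortality in patients receiving dialysis (56), subjects will be stratified by receipt of dialysis". The same paragraph also states: "Receipt of dialysis has no effect on CMV disease rate in transplant recipients".

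Section 12.5.4 gives the primary analysis as a CMH test and lists no strata. It then says: "The analysis will be repeated, controlling for induction antilymphocyte therapy". The within-stratum results it promises can therefore only be by induction. The other repeats change something else: losses to follow-up counted as disease (12.5.4), the modified ITT population (12.5.5), and the source of the endpoint (12.5.6). None adds dialysis.

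Section 12.6.1.1 calls its CMH of adjudicated CMV disease at 3 and 12 months similar to the primary analysis, but runs it "while controlling for the use of induction antibody therapy and renal dialysis". Dialysis is also controlled for in rejection (12.6.1.4), graft loss (12.6.1.5), neutropenia (12.6.2.1) and time to CMV disease (12.7.1.1).

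**The concern.** A trial that balances its arms within strata has removed the between-stratum part of the chance difference between arms. An analysis that ignores the strata still counts that part as noise. If a stratum predicts the outcome, the test is conservative and loses some power.

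Dialysis could predict the endpoint as analysed even if it does not change the CMV rate. Section 12.5.4 counts death without CMV disease as no disease, and 2.2.2 says dialysis patients die more often.

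There is also a consistency problem. Section 12.5.6 repeats the primary CMH on adjudicated disease without dialysis, while the text of 12.6.1.1 analyses adjudicated disease at 12 months with it. The report could carry two p-values for nearly the same question that differ only because of an unstated choice of strata.

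**Working it through.** **1. The plan's own sample size.** Section 12.1 assumes 20% versus 5%, two-sided alpha 0.05, power 80%, and gives 160 subjects. By Freedman's log-rank formula, HR = ln(0.95)/ln(0.80) = 0.230. Events = (1.960 + 0.842)² × [(1 + 0.230)/(1 − 0.230)]² = 20.0, and 20.0/0.125 = 160. The figure reproduces. Exact Fisher power at 80 per group is 79.3%.

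**2. Assumed inputs.** The documents give no dialysis share, induction share or numeric stratum effect. Assume 20% for each share, independent, with N = 176 (the minimum enrollment in section 4). The weights for neither / induction only / dialysis only / both are 0.64 / 0.16 / 0.16 / 0.04. Prophylaxis-arm risks in the same order:

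| Scenario | Risks | Induction risk ratio | Dialysis risk ratio |
|---|---|---|---|
| Strong | .16 / .45 / .10 / .30 | 2.8-3.0 | 0.63-0.67 |
| Moderate | .17 / .34 / .12 / .24 | 2.0 | 0.71 |
| Weak | .20 / .20 / .14 / .14 | 1.0 | 0.70 |

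The weighted average risks are 20.2%, 19.2% and 18.8%, close to the plan's 20%.

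**3. Size of the conservatism by hand, strong scenario under the null.** With 1:1 balance in every stratum, the stratified and unstratified CMH have the same numerator and differ only in variance.
- Unstratified, per subject: 0.2024 × 0.7976 = 0.1614.
- Within four strata: .64(.16)(.84) + .16(.45)(.55) + .16(.10)(.90) + .04(.30)(.70) = 0.1484.
- Ratio 0.1484/0.1614 = 0.919, square root 0.959. The effective critical value is 1.96/0.959 = 2.04, a two-sided level of about 4.1%.

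Share of the variance due to each factor:
- Induction: mean risks 0.148 without and 0.420 with. 0.8 × 0.2 × 0.272² = 0.0118, or 7.3% of 0.1614.
- Dialysis: mean risks 0.218 without and 0.140 with. 0.8 × 0.2 × 0.078² = 0.0010, or 0.6%.

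**4. Simulation, 200,000 trials per scenario, CMH without continuity correction.** Strong scenario, percent of trials rejecting:

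| Treatment risk ratio | Unstratified | Induction only | Dialysis only | Four strata |
|---|---|---|---|---|
| 1 (null) | 4.0 | 4.9 | 4.1 | 5.0 |
| 0.25 | 89.4 | 90.0 | 89.4 | 90.1 |
| 0.35 | 74.4 | 75.9 | 74.6 | 76.2 |

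The largest gain is 76.2 − 74.4 = 1.8 points. Induction alone supplies 75.9 − 74.4 = 1.5. Dialysis adds 0.2 to the unstratified test (74.6 − 74.4) and 0.3 to the induction-controlled one (76.2 − 75.9). The moderate scenario gains 0.3-0.6 point and the weak one about 0.1. Across the three scenarios the unstratified null rate is about 4.0-4.8% and the four-stratum rate about 5.0%.

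**5. Dialysis varied alone.** 80 per group, overall rates held at 20% and 5%, dialysis share 10-30%.

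| Dialysis risk ratio | Power, unstratified | Power, stratified by dialysis |
|---|---|---|
| 1 (as 2.2.2 states) | .849-.850 | .850-.851 |
| 0.5 | .849-.850 | .850-.852 |
| 3 | .854-.858 | .861-.867 |

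The route through deaths pushes the dialysis risk ratio below 1, where the gain is at most 0.2 point. Only an assumed ratio of 3 gives about 0.9 point, with unstratified type I error near 4.4%. Nothing in the documents suggests such a ratio.

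**The case against.** The strongest reply is that dialysis hardly matters here. Section 2.2.2 says it does not affect the CMV disease rate, and the calculations put its contribution at a few tenths of a point. That stands. What the unstratified test gives up is almost wholly due to induction, for which 12.5.4 already plans a repeat.

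It can also be said that a CMH test implies strata, so 12.5.4 is merely terse. But a separate repeat for induction makes sense only if the first run has no induction stratum, and no sentence in 12.5 brings in dialysis.

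Four stronger readings are tempting, and the documents do not support them.
- That dialysis patients were admitted on condition of a stratified analysis. Section 2.2.2 includes them for representativeness and presents stratification as a response to their mortality. Stratified randomization meets that commitment.
- That dialysis never enters an analysis of CMV disease. It does so in 12.6.1.1 and in the Cox and stratified log-rank analyses of 12.7.1.1.
- That the primary test is invalid. The error is towards too few rejections.
- That the analyses use different induction variables. Section 12.6.1.3 does say "the analysis will be repeated using a CMH test stratified by receipt of induction therapy", but later names anti-lymphocyte induction with dialysis. This is loose wording, with no sign of a second variable.

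**Conclusion.** The point holds as an inconsistency in the specification of the primary analysis, with a small cost. Both randomization factors belong in the primary CMH. The plan uses neither in the primary test and only one in its adjusted repeat.

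Under the assumed 20%/20% shares and the three sets of stratum risks, the unstratified test runs at about 4.0-4.8% instead of 5% and loses 0 to about 1.8 points of power. Dialysis accounts for about 0.1-0.3 point of that. Four-stratum analysis lost no power in any scenario. The sample size of 160 evaluable subjects does not change, and type I error is not inflated. The shares and stratum effects are assumptions; the mismatch between 12.5.4 and 12.6.1.1 is not.

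One caution on that mismatch: 12.6.1.1 is headed as late-onset disease, while its text covers incidence at 3 and 12 months. The near-duplication rests on the text.

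**What to change.** In 12.5.4, define the primary analysis as the CMH test with the Mantel-Haenszel estimate, stratified by lymphocyte-depleting induction (yes/no) and dialysis (yes/no), using the levels recorded at randomization. Section 12.6.2.1 already has that rule for neutropenia and can be copied. Keep the unstratified CMH as a supportive result, and let 12.5.5 and 12.5.6 inherit the same strata.

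State that site, although randomization is stratified within it, is left out of the strata because cells would be sparse. Six sites by four strata make 24 cells, or 176/24 = 7.3 subjects on average. At the assumed shares, the cell with both dialysis and induction would hold 176 × 0.04 = 7 subjects over all sites, about one per site.

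Use the same factor definition in 12.6.1.1 and 12.6.1.3.

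The cost is wording only. Both factors are needed to randomize a subject, so no new data are required and the sample size is untouched.
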